#### **Appendix VI Pharmacogenomics**

All research performed with the samples during this study is ruled by the provisions of Law 14/2007 of biomedical research and RD 1716/2011 of November 18 which sets the basic requirements for authorization and running of biobanks for purposes of biomedical research y handling of human biological samples.

Subjects enrolled in this clinical study will have samples collected for pharmacogenomic and biomarker analysis. The aim of the analysis is to identify genetic factors that may influence a subject's exposure to the study drug, as well as genetic factors that may have an effect on clinical response or potential adverse events related to study treatment, and to explore the role of genetic variability in response. Samples may be analyzed to determine a subject's genotypes or sequence for a number of genes or non-coding regulatory regions. The research may include the investigation of polymorphisms in genes that are likely to influence the study drug pharmacokinetics or therapeutic response.

Collection of the samples for pharmacogenomic analysis will be bound by the sample principles and processes outlined in the main study protocol. Sample collection for pharmacogenomic and biomarker analysis is required as per the study protocol unless the collection and use of the samples is prohibited by specific country laws.

The patients will sign a specific Informed Consent form for the sample pharmacogenomic collection.

#### SAMPLE COLLECTION AND HANDLING

The samples will be collected according to the study flow chart and laboratory manual.

The sponsor of the study may decide not to conduct any pharmacogenomics analysis of the samples collected during the study if its primary efficacy endpoint is not achieved and there are not clinically relevant safety issues that raise additional interest. This decision will be notified to all IEC and regulatory authorities.

#### SECURITY OF THE SAMPLES, USE OF THE SAMPLES, RETENTION OF THE SAMPLES

Sample processing, including DNA/RNA extraction and genotyping, sequencing or other analysis will be performed by a laboratory under the direction of the study sponsor. Processing, analysis, and storage will be performed at a secure laboratory facility to protect the validity of the data and maintain subject privacy.

The laboratory in charge of processing, storing and destroying the samples is Laboratory of Hospital Vall Hebrón; [name].

Samples will only be used for the purposes described in this protocol by the study sponsor. Laboratories contracted to perform the analysis on behalf of the study sponsor will not retain rights to the samples beyond those necessary to perform the specified analysis and will not transfer or sell those samples. The study sponsor will not sell the samples to a third party and will not

Page 86 of 88 Date: April 04th, 2016

transfer them. Samples will be stored for up to 15 years after the completion of the study (defined as submission of the clinical study report [CSR] to the appropriate regulatory agencies). At the end of the storage period, samples will be destroyed. Samples may be stored longer if a Health Authority (or medicinal product approval agency) has active questions about the study. In this special circumstance, the samples will be stored until the questions have been adequately addressed.

It is possible that future research and technological advances may identify genomic variants of interest, or allow alternative types of genomic analysis not foreseen at this time. Because it is not possible to prospectively define every avenue of future testing, all samples collected will be single-or double-coded (according to the ICH15 guidelines) in order to maintain subject privacy.

#### **RIGHT TO WITHDRAW**

If, during the time the samples are stored, a participant would like to withdraw his/her consent for participation in this research. The study sponsor will destroy the samples, if they can still be identified (not anonymized). Once samples have been anonymized, it will not be possible to identify which samples have come from a particular individual. Therefore, it will not be possible to destroy subject samples after anonymization. Information from any assays that have already been completed at the time of withdrawal of consent will continue to be used as necessary to protect the integrity of the research project.

#### SUBJECT PRIVACY AND RETURN OF DATA

No subject-identifying information (e.g., initials, date of birth, government identifying number) will be associated with the sample. Samples that are processed for analysis (DNA/RNA extracted) may be double-coded. Double-coding involves removing the initial code and replacing with another code such that the subject can be re-identified by use of 2 code keys. The code keys are usually held by different parties. The key linking the sample ID to the subject number will be maintained separately from the sample. At this point, the samples will be double-coded (the first code being the subject number) as long as the initial tube does not carry any personal identifiers or the random code assigned by the central laboratory or biorepository.

Laboratory personnel performing genetic analysis will not have access to the "key." Clinical data collected as part of the clinical trial will be cleaned of subject identifying information and linked by use of the sample ID "key."

Sample anonymization may occur by destruction of the "key." Once the "key" is destroyed, it will not be possible to trace the pharmacogenomics assay results back to an individual. The sponsor will take steps to ensure that data are protected accordingly and confidentiality is maintained as far as possible. Data from subjects enrolled in this study may be analyzed worldwide, regardless of location of collection.

The sponsor and its representatives and agents may share anonymized data with persons and organizations involved in the conduct or oversight of this research. These include:

- Clinical research organizations retained by the sponsor;
- Independent ethics committees or institutional review boards that have responsibility for this research study;
- National regulatory authorities or equivalent government agencies

At the end of the analysis, results may be presented in a final report which can include part or all of the anonymized data, in listing or summary format. Other publication (e.g., in peer-reviewed scientific journals) or public presentation of the study results will only include summaries of the population in the study, and no identified individual results will be disclosed.

Given the research nature of the planned analysis, it will not be possible to return individual data to subjects participating in the pharmacogenomics analysis.

Page 88 of 88 Date: April 04th, 2016

# Appendix VII: Adverse event report form

Please see attached form

EudraCT no.: 2015-001467-39

	Lenvatinib will be provided as 4-size hydroxypropyl methylcellulose (HPMC) capsules in 2 strengths differentiated by color: 4-mg capsule (yellowish-red cap and body) and 10-mg capsule (yellowish-red cap with yellow body). Dosing schedule of 24 mg once a day (two 10-mg capsules + one 4-mg capsule) has been selected for continued lenvatinib	
	development.	
Trial phase	II	
Objectives	Primary objective To assess the efficacy of lenvatinib on tumor objective response rate in two independent cohorts of patients with advanced neuroendocrine tumors: patients with advanced/metastatic G1/G2 pancreatic neuroendocrine tumors after progression to a previous targeted agent (cohort A), and patients with advanced/metastatic G1/G2 neuroendocrine tumors of gastrointestinal tract after failure to somatostatin analogues therapy (cohort B). Secondary objectives To determine the safety and tolerability of lenvatinib. To estimate the early tumor shrinkage rate and the deepness of response of lenvatinib in each cohort of patients. To estimate progression-free survival in both cohorts of patients. Exploratory objectives To evaluate biochemical response (changes in CgA and NSE levels) and its association with response rate and progression-free survival. To assess whether baseline tumor and blood biomarkers may be predictive of response to lenvatinib. To explore additional hypotheses related to biomarkers and relationship to lenvatinib, neuroendocrine tumors, other	

Page 5 of 16 Date: June 04, 2020

TALENT Statistical Analysis Plan	Version 2.0 Date: June 04, 2020		
	endocrine disorders and/or cancer which may arise from internal or external research activities.		
Design	Prospective, international, multi-center, open label, stratified, exploratory phase II study evaluating the efficacy and safety of lenvatinib.		
Primary endpoint	The primary endpoint of the study is overall response rate (ORR) by RECIST v 1.1 upon central radiologic assessment.		
Study population and total number of subjects	Patients with advanced/metastatic, histologically confirmed, grade 1/2 (G1/G2) of 2010 WHO classification neuroendocrine tumors of the pancreas after progression to a previous targeted agent (cohort A) or gastrointestinal tract after progression to somatostatin analogues (cohort B). Number of patients: 110 patients in total (55 per each cohort).		
Approximate duration of subject participation	24 months		
Calendar and estimated completion dates	Recruitment Start: September 2015 End of Recruitment Period: March 2017 3rd Tumor assessment of LP (Primary Analysis): July 2017 Database Lock for Interim Analysis: October 2017 End of Follow up Period: March 2019 FPFV: September 2015 LPLV: September 2018 Clinical Study Report: September 2019		

2. Tab	ole of contents	
1. Sy	nopsis	3
2. Tal	ble of contents	6
3. Ab	breviations	7
4. Stu	ıdy objectives and variables	8
4.1	Primary objective(s) and primary variable(s)	
4.2	Secondary objective(s) and secondary variables	
	secondary objective(s) and secondary variables	
4.3	Exploratory objective(s) and variables	
The e	exploratory objectives are:	
	pratory variables:	
	idy populations	
	itistical strategy	
6.1		
6.1.1	Primary analysisSummary statistics	
6.1.2	Statistical inference	
6.2	Secondary analysis	
	econdary analysis will be based on the Full Analysis Set and the Safety Ana	
Set		
6.2.1	Summary statistics	11
6.2.2	Statistical inference	12
6.3	Exploratory analysis	12
6.4	Subgroup analysis	12
6.5	Safety analysis	13
6.5.1	Summary statistics	
6.5.2	Statistical inference	
6.6	Demographic and baseline characteristics	
6.7	Concomitant medications	
6.8	Statistical significance level	
6.9	Statistical model assumptions	
6.10	Transformation of expected variables	
6.11	Handling of missing data	
6.12	Description of the softwares to be used for data analysis	
6.13	Interim analysis protocol	
7. Ref	ferences	16

Confidential Version 2.0

GETNE
TALENT Statistical Analysis Plan

Page 7 of 16 Date: June 04, 2020

3. Abbreviations

AE:

Adverse Event

CgA:

Chromogranin A

CR:

Complete Response

DpR:

Deepness of Response

ECG:

Electrocardiogram

eCRF:

electronic Case Report Form

ETS:

Early Tumor Shrinkage

G1:

Grade 1

G2:

Grade 2

GETNE:

Grupo Español de Tumores Neuroendrocrinos

HPMC:

Hydroxypropyl Methylcellulose

NSE:

Neuron Specific Enolase

OOR:

Objective Response Rate

OS:

Overall Survival

PFS:

Progression-Free Survival

PI:

Principal Investigator

PR:

Partial Response

RECIST:

Response Evaluation Criteria In Solid Tumors

SAE:

Serious Adverse Event

WHO:

World Health Organization

4. Study objectives and variables

4.1 Primary objective(s) and primary variable(s)

To assess the efficacy of lenvatinib on tumor objective response rate (ORR), complete (CR) and partial responses (PR) in two independent cohorts of patients with advanced/metastatic G1/G2 neuroendocrine tumors: patients with pancreatic neuroendocrine tumors after progression to a previous targeted agent (cohort A), and patients with neuroendocrine tumors of the gastrointestinal tract after failure to somatostatin analogues therapy (cohort B).

The ORR is defined as the proportion of subjects who have best overall response of CR or PR (by RECIST criteria):

$$ORR = \frac{CR + PR}{Total \ of \ patients}$$

4.2 Secondary objective(s) and secondary variables

The secondary objectives are:

- To determine the safety and tolerability of lenvatinib.
- To estimate the early tumor shrinkage rate and the deepness of response of lenvatinib in each cohort of patients.
- To estimate progression-free survival in both cohorts of patients.

Secondary variables:

- To determine the safety and tolerability of lenvatinib. Safety will be assessed by adverse events (AEs) and serious adverse events (SAEs). Echocardiogram results (LVEF reductions) and QTc (using the QTcB and QTcF values) prolongations will be examined. QTc prolongation will be examined through the adverse events.
- To estimate the early tumor shrinkage (ETS) rate and the deepness of response
 (DpR) of lenvatinib in each cohort of patients:
 - ETS rate is defined as 20% reduction in target lesions after the first 6 weeks of treatment (first tumor assessment).
 - DpR is defined as percentage of maximum tumor shrinkage observed at the nadir (minimum value of total sum of diameters) compared with baseline.

To assess ETS and DpR, total sum of diameters obtained in all tumor assessments will be considered.

• To estimate progression-free survival (PFS) in both cohorts of patients. PFS is defined as the time from the date of treatment start (C1D1) to the date of first documentation of disease progression or death (whichever occurs first) using RECIST 1.1.

Page 9 of 16 Date: June 04, 2020

To evaluate PFS, it will be considered:

- Start date of study drug
- o Progression disease date or death date (whichever comes first)

PFS censoring rules will follow FDA guidance in 2007 [1]:

Table A. PFS 1 (includes documented progression only)

Situation	Date of Progression or Censoring	Outcome
No baseline tumor assessments	Randomization	Censored
Progression documented between scheduled	Earliest of:	Progressed
visits	 Date of radiological assessment showing new lesion (if progression is based on new lesion); or Date of last radiological assessment of measured lesions (if progression is based on 	
	increase in sum of measured lesions)	6 1
No progression	Date of last radiological assessment of measured lesions	Censored
Treatment discontinuation for undocumented progression	Date of last radiological assessment of measured lesions	Censored
Treatment discontinuation for toxicity or other reason	Date of last radiological assessment of measured lesions	Censored
New anticancer treatment started	Date of last radiological assessment of measured lesions	Censored
Death before first PD assessment	Date of death	Progressed
Death between adequate assessment visits	Date of death	Progressed
Death or progression after more than one missed visit	Date of last radiological assessment of measured lesions	Censored

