#### Tumor assessments

- Tumor assessments will be performed using RECIST 1.1. (Appendix I) Investigator determined response assessments will be performed at each assessment time point and entered onto the eCRF. Copies of all tumor imaging studies will be sent to an imaging core laboratory (Central Review) for prospective on-study primary efficacy assessment. Tumor assessments will be carried out following the guidelines provided by the study sponsor. Tumor assessments (CT of abdomen, and pelvis, and of all other known sites of disease) will be performed during the screening phase and, the first assessment will be performed 6 weeks after the first dose, the second assessment will be performed 12 weeks after the first dose, then every 12 weeks during study treatment cycles in the treatment phase or sooner if clinically indicated until documentation of disease progression.
- A brain CT/MRI will be performed at screening, as clinically indicated. In addition, for subjects with history of treated brain metastases, brain scans must be performed at screening and every tumor assessment time point.

- Page 38 of 88 Date: April 04th, 2016
- Data from somatostatin receptor schintigraphy or PET-CT (octreoscan) with specific radiolabeled agents for neuroendocrine tumors (such as Ga68, 5-HTP or F-Dopa) will be collected if available and performed within the 6 months prior to the first dose of study drug but are not acceptable as tumor assessment techniques during treatment phase.
- Data from bone scan will be collected, if available and performed within 6 months prior
  to first dose of study drug and every 24 weeks after first dose of study drug, and at the
  final visit unless the last scan was performed less than 24 weeks before.
- Somatostatin schintigraphy, PET and bone scan are not compulsory. They will be collected, if performed.
- A chest x-ray or skeletal x-ray that clearly demonstrates a new metastatic lesion may be used to document progression in lieu of the CT/MRI scans.
- Subjects who discontinue study drug prior to disease progression must continue to undergo tumor assessments every 12 weeks in the follow-up period, until disease progression is documented or another anti-cancer therapy is initiated.

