6.1.1 Summary statistics

The ORR will be calculated by RECIST v1.1 upon central radiologic assessment, independently for each cohort.

Waterfall plots (2D and 3D) will be calculated to examine the changes in tumor lesions from baseline.

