6.2.1 Summary statistics

Secondary endpoints will be summarized with descriptive statistics. Continuous variables will be summarized with n, NA, mean, standard deviation, median and range. Frequency counts and percentage of subjects within each category will be provided for categorical data.

First secondary objective:

Safety analyses will be based on the Safety Analysis Set. All safety analyses will be summarized separately by cohort.

Adverse events will be classified into standardized medical terminology from the verbatim description (investigator term) using the Medical Dictionary for Regulatory Activities (MedDRA). Adverse events will be presented by preferred term (PT) and by system organ class (SOC).

Echocardiogram results (LVEF), and their changes from baseline will be summarized using descriptive statistics. Prolongation of QTc will be analysed using descriptive statistics and frequency tables.

The degree of exposure (dose, duration of treatment, interruptions/reductions of dose) will be assessed to determine the degree to which study safety can be assessed. These results will be presented with descriptive statistics (n, NA, mean, standard deviation, median and range).

Second secondary objective:

The ETS and DpR will be calculated for each cohort. Both ratios will be calculated using the total sum of diameters provided in tumor assessments by central radiology review.

Third secondary objective:

PFS will be calculated using start date of study drug and progression disease or death date (whichever occurs first), based on the Full Analysis set and Per-protocol Analysis Set. PFS censoring rules will follow FDA guidance in 2007 (see Table A).

OS will be calculated using start date of study (C1D1).

A Kaplan Meier survival analysis will be carried out to analyse PFS, providing the median and the corresponding 95% CI of time to progression. Survival curves will be reported.

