6.11 Handling of missing data

No planned procedure of imputation of missing values. The analysis will be performed with the available data.

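### The ETS rate has no stated denominator, and the available-data rule drops patients without a week-6 scan, which tends to overstate the rate

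*SAP*

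**What the plan says.** **ETS.** SAP 4.2 states: "ETS rate is defined as 20% reduction in target lesions after the first 6 weeks of treatment (first tumor assessment"). SAP 6.10 repeats the threshold. Neither section names a denominator or says what happens when the week-6 sum is absent or late. For ORR, by contrast, SAP 4.1 writes out a formula that divides by the total number of patients.

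**DpR.** SAP 4.2 states: "DpR is defined as percentage of maximum tumor shrinkage observed at the nadir (minimum value of total sum of diameters) compared with baseline". A sentence covering both measures follows: "To assess ETS and DpR, total sum of diameters obtained in all tumor assessments will be considered". SAP 6.2.1 fixes the reader: "Both ratios will be calculated using the total sum of diameters provided in tumor assessments by central radiology review".

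**Analysis set.** SAP 6.2 bases secondary analyses on the Full Analysis Set (and the Safety Analysis Set). SAP 5 defines the Full Analysis Set as all allocated subjects. Only the Per Protocol set requires a post-baseline tumor assessment.

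**Missing values.** SAP 6.11: "No planned procedure of imputation of missing values. The analysis will be performed with the available data". Protocol 20.7 tells the analyst to disregard missing data. For the primary endpoint it keeps patients who are lost or stop treatment only if they have had at least one tumor assessment.

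**Imaging.** Protocol 12.2 schedules scans at weeks 6 and 12 and every 12 weeks after that, "or sooner if clinically indicated until documentation of disease progression". Protocol 7.3 also ends imaging when another anticancer therapy starts.

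**The concern.** ETS depends on one scan. A patient who dies, deteriorates clinically, switches therapy or leaves the study before that scan has no week-6 sum. Under the available-data rule this patient is neither a success nor a failure but simply absent. Absence is likely to be related to outcome, because most of these events are treatment failures.

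The result would carry the Full Analysis Set label while resting on a scan requirement close to that of the Per Protocol set. It would also use a different denominator from the ORR formula, so the two rates could not be set side by side for the same cohort. A reader comparing the cohorts, or comparing either with another study, could not tell how much of a difference came from the patients left out.

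**Working it through.** **The plan's own figure.** The documents give no expected value for ETS or DpR. The only design figure is 55 per cohort for ORR (Protocol 20.6: 10% against 25%, 90% power, 5% level). An exact one-sided single-stage binomial search reproduces it: the smallest n reaching 90% power is 55, declaring success at 10 or more responses, with alpha 0.0444 and power 0.911. Here it supplies only N = 55.

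**Inputs.** N = 55 per cohort (Protocol 20.6). The number m without a usable week-6 sum is not in the documents; 3, 6 and 8 are assumed, with 11 (20% of 55) as a stress case. The ETS rate is also not in the documents; 30% (16.5/55) is assumed, and 14 of 55 is used as a whole-number example.

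**Step 1: ETS.** Let E be the number of patients with ETS. Over all allocated patients the rate is E/55. On available data it is E/(55 − m). If none of the m had ETS, the ratio of the two is 55/(55 − m).

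| m | 55/(55−m) | 30.0% is reported as | 14/55 = 25.5% is reported as |
|---|---|---|---|
| 3 | 1.06 | 16.5/52 = 31.7% | 14/52 = 26.9% |
| 6 | 1.12 | 16.5/49 = 33.7% | 14/49 = 28.6% |
| 8 | 1.17 | 16.5/47 = 35.1% | 14/47 = 29.8% |
| 11 | 1.25 | 16.5/44 = 37.5% | 14/44 = 31.8% |

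**Step 2: against sampling error.** The standard error of a 30% rate is √(0.30 × 0.70/55) = 6.2 points. The shifts at m = 3 and m = 8 are 1.7 and 5.1 points, about 0.3 and 0.8 of a standard error.

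**Step 3: dependence on who is missing.** The factor in step 1 is an upper limit. If 1 of 8 missing patients would have shown ETS, the all-patient rate is 17.5/55 = 31.8% and the overstatement falls from 5.1 to 3.3 points. If the missing shrink as often as the scanned, there is no bias.

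**Step 4: can the week-6 scan be missed after stopping treatment?** Protocol 7.3 keeps the week-6 scan for a patient who stops drug without progression. Protocol 18.1 instead counts every 12 weeks from the last assessment. For a patient who stops before week 6 the last assessment is the screening scan, so that wording can pass over week 6. The two sections need to be reconciled.

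**Step 5: the DpR wording.** If the screening scan may serve as the nadir, a patient whose lesions only grow scores 0. If the nadir must be post-baseline, the score is negative. Suppose best shrinkage is normal with mean μ and SD 20 (assumed). Scoring growth as 0 gives a mean of μΦ(μ/20) + 20φ(μ/20): 14.0 for μ = 10, 17.6 for μ = 15, 21.7 for μ = 20 and 26.0 for μ = 25. The difference is 1.0 to 4.0 points in the mean. The median does not move unless about half of the patients only grow, and ETS cannot be affected.

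**The case against.** The strongest reply is that SAP 6.11 is a general statement against imputation. It does not mention ETS, and SAP 6.2 with SAP 6.2.1 could be read as percentages of all allocated subjects. That reading is possible, but nothing in SAP 4.2, 6.2.1 or 6.10 says that a patient without a scan counts as no ETS. The only instruction on absent values points the other way.

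A second reply is that some early failures keep a value. Progression on an earlier unscheduled scan may count as the first tumor assessment, and progression found at the week-6 scan itself supplies a sum. This stands and makes m smaller. For the same reason, m should not be derived from the median PFS figures in Protocol 5.2.2. They come from a thyroid-cancer trial, one of them from its placebo arm, and a PFS event by week 6 is not the same as a missing scan.

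A reader might infer that both endpoints are inflated because growth is scored as 0 in DpR. The documents do not support that. SAP 4.2 states no floor, compares the nadir with baseline, and calls week 6 the first assessment; SAP 6.13 and Protocol 7.4 likewise treat week 12 as the second. Usage is mixed, since Protocol 12.2 also places tumor assessments in the screening phase, so the text is ambiguous and no more. Nor does a missed week-6 scan remove a patient from DpR, which can use later scans; only a patient with no post-baseline sum is lost. For continuous endpoints SAP 6.2.1 already requires the number not available.

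**Conclusion.** The point holds for ETS. Followed as written, the plan gives an available-case rate under an all-allocated label, and the likely direction of error is upward. The size is modest: 1.7 to 5.1 points on a 30% rate for 3 to 8 missing scans in a cohort of 55. It rests on an assumed ETS rate, an assumed number missing, and the premise that none of the missing had ETS.

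For DpR the finding is only that the text permits two calculations. Inflation is not shown.

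Both endpoints are secondary and descriptive, with no threshold or decision rule, and neither the ORR formula nor the sample size is affected. The change is worth making because it is cheap and brings ETS into line with the ORR denominator.

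**What to change.** In SAP 4.2 and 6.10:

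1. Compute the ETS rate over the Full Analysis Set in each cohort.
2. Count as no ETS any patient without a week-6 sum because of death, progression, new anticancer therapy or discontinuation. Count progression on an earlier unscheduled scan as no ETS. For new therapy this agrees with Protocol 11.10, which already treats additional anti-tumor therapy as evidence of progression.
3. Say how a late week-6 scan is handled. Show separately the number whose scan is missing for any other reason.
4. Give the scanned-only rate as a secondary figure.

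As a minor clarification, define DpR as 100 × (baseline sum − smallest post-baseline sum)/baseline sum, centrally read and with its sign. Growth is then negative and agrees with the waterfall plots that SAP 6.1.1 plans "to examine the changes in tumor lesions from baseline".

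The cost is a few sentences in the SAP and an extra row or two in the ETS table. No new data are needed. The downside is a slightly less favourable ETS rate and, if the screening scan would otherwise have been allowed as the nadir, a slightly lower mean DpR.

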#### 7.3 Treatment phase

The treatment phase will begin at the time of allocation of the first subject and will consist of the study treatment cycles. The treatment phase will end when the last patient discontinues the study drug. Prior to the completion of the final primary study analysis, an individual subject will remain in the treatment phase until documentation of disease progression.

Subjects who discontinue study drug administration prior to disease progression will continue to be followed in the treatment phase according to the tumor assessment schedule listed in table 3 (performed at week 6 after the first dose of study drug and then, every 12 weeks or sooner if clinically indicated) until documentation of disease progression or start of another anticancer therapy.

Subjects will be allocated in each primary tumor cohort to receive lenvatinib 24 mg by continuous once daily oral administration. Subjects will undergo safety and efficacy assessment as defined in Table 3. Other reasons for discontinuation of study drug different from disease progression include development of unacceptable toxicity, withdrawal of consent or sponsor discontinuation of lenvatinib development.

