6.10 Transformation of expected variables

• The ORR is defined as the proportion of subjects who have best overall response of CR or PR (by RECIST 1.1):

- The time to progression is defined as the difference between start of drug (C1D1) and the progression date or death (whichever occurs first) or the last tumor assessment documented.
- ETS rate is defined as 20% reduction in target lesions after the first 6 weeks of treatment.
- DpR is defined as percentage of maximum tumor shrinkage observed at the nadir (the minimum of total sum of diameters) compared with baseline.
- Overall survival is defined as the time from the start of drug (C1D1) to death.

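### DpR has no cut at central progression, so a scan made after central but before site progression can set the nadir (SAP 4.2)

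*SAP*

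**What the plan says.** SAP 4.2 defines DpR as the greatest shrinkage from baseline, taken at the smallest sum of diameters, and then names the data: "To assess ETS and DpR, total sum of diameters obtained in all tumor assessments will be considered". SAP 6.2.1 fixes the reader for ETS and DpR: "Both ratios will be calculated using the total sum of diameters provided in tumor assessments by central radiology review". SAP 6.10 repeats the definition: "DpR is defined as percentage of maximum tumor shrinkage observed at the nadir (the minimum of total sum of diameters) compared with baseline". Protocol 12.3 defines DpR in the same way. None of these places ends the window at progression.

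The protocol sets when scanning stops. Under 7.3, "an individual subject will remain in the treatment phase until documentation of disease progression". Under 12.2, scans fall at weeks 6 and 12 and then every 12 weeks until progression is documented. Patients who stop the drug earlier are scanned until progression or another anticancer therapy (7.3, 7.3.1, 12.2, 18.1).

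Two readings run in parallel under Protocol 12.2. At the site: "Investigator determined response assessments will be performed at each assessment time point and entered onto the eCRF". Centrally: "Copies of all tumor imaging studies will be sent to an imaging core laboratory (Central Review) for prospective on-study primary efficacy assessment".

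**The concern.** The sums used for DpR are central reads, but the event that ends scanning is not tied to the central reading. If the central reader sees progression before the site does, the patient stays on the routine schedule. The later scans also go to central review, and the SAP tells the programmer to use all of them. A patient who has already progressed by central review can then be credited with shrinkage reached afterwards.

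This matters mainly when progression comes from a new or non-target lesion, because the target sum may still be falling. The SAP expects such cases: Table A has an entry for "Date of radiological assessment showing new lesion (if progression is based on new lesion". DpR is a stated secondary objective in each cohort, and any error would run one way, towards a deeper response.

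**Working it through.** **The plan's own figure.** The documents give no figure for DpR. The only design figure is 55 patients per cohort (Protocol 20.6: 10% against 25%, 90% power, 5% level). An exact single-stage binomial search reproduces it: n = 55 with success at 10 or more responses has one-sided alpha 0.0444 and power 0.9112, and no smaller n meets both limits. The DpR point does not depend on it.

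**Whose progression ends scanning?**
- Protocol 7.3, 7.3.1, 12.2 and 18.1 stop scans when progression is documented. None names the reader.
- Protocol 12.2 has the site call response at every time point and describes central review as prospective, for the primary efficacy assessment. Protocol 15.1 sends the images to an independent radiologist. Neither section returns the result to the site or lets it end scanning.
- SAP 4.2, 6.2.1 and 6.10 take the minimum over all centrally read sums.

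So a centrally read scan after central progression is possible under the text, and the SAP includes it.

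**Direction.** A minimum over a larger set of scans is equal to or below the minimum over a subset. Extra scans can only leave DpR unchanged or deepen it.

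**Number of scans.** The schedule in Protocol 12.2 gives weeks 6, 12, 24 and 36. Suppose central progression is at week 12:
- cut at central progression: weeks 6 and 12, so 2 scans;
- site call at week 24: 3 scans;
- site call at week 36: 4 scans.

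**One patient (assumed sums in mm).** DpR = 100 × (baseline − minimum) / baseline.
- Central progression by new lesion at the third post-baseline scan: 100, then 85, 80, 78 (progression), 70. All scans: 100 − 70 = 30%. Cut at and including progression: 100 − 78 = 22%.
- Central progression by target growth at the third post-baseline scan: 100, then 75, 70, 85 (progression, 85/70 = +21%), 66. All scans: 34%. With the cut: 30%.

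The second route is harder. Take 20% growth over the nadir as target progression (an input here; the protocol adopts RECIST 1.1 by reference and does not print the threshold). A later sum must then fall by more than 1 − 1/1.2 = 16.7% from the progression value to become a new nadir. After progression by a new lesion, any sum below the earlier minimum is enough.

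**Cohort mean.** If all 55 patients have post-baseline sums, the shift is k × d / 55, where k patients have a nadir d points deeper. The documents give neither k nor d; both are assumptions.

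| k | d = 10 | d = 25 |
|---|---|---|
| 1 | 10/55 = 0.18 | 25/55 = 0.45 |
| 3 | 30/55 = 0.55 | 75/55 = 1.36 |
| 5 | 50/55 = 0.91 | 125/55 = 2.27 |

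**The case against.** The strongest reply is that the protocol already bounds the data. Scanning ends at documented progression, so all tumor assessments means all scans in that bounded schedule. The SAP sentence also governs ETS, which needs only the week 6 scan, so it may have been meant to name the measurement and not to open a window. What remains needs several things in one patient: central progression before the site's call, no action on the central reading, and a later sum below every earlier one. That central results are not fed back is an inference from silence. Protocol 12.2 refers to sponsor guidelines for tumor assessment, which are not among these documents and could settle it. Finally, target shrinkage that continues after a centrally read new lesion is real, and one could choose to count it.

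Most of this stands as a limit on size. It does not remove the problem, because no section makes the central reading the stopping event, and a programmer following the SAP literally would use every central sum.

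Two stronger readings are tempting and do not hold.
- Table A censors PFS at "New anticancer treatment started" and DpR has no such line, so a reader might infer that scans after new therapy feed DpR. The protocol closes this at collection. Section 11.10 treats other anti-tumor therapy as evidence of progression, stops the drug and moves the patient to survival follow-up. Sections 7.3, 7.3.1, 12.2 and 18.1 stop scans at new therapy. PFS needs a censoring date; a minimum over collected scans does not.
- Protocol 7.1 lets treatment continue while there is clinical benefit, so a reader might infer that scanning runs on past progression as a rule. Sections 7.3 and 12.2 end it at documented progression, so 7.1 does not extend it.

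**Conclusion.** The point holds in a narrow form and is minor. As written, a scan made after central progression but before the site's call can set the nadir, and it can only deepen DpR. This arises only if the two progression dates differ with the central one first, and if the central result does not stop scanning. The documents neither state nor exclude the second condition.

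The size cannot be derived from the documents and is probably small. The table above is for scale only, and five affected patients in a cohort has no support in the text. SAP 6.2.1 also reports the median, which a few patients would move little. DpR has no threshold, test or decision rule. The waterfall plots in SAP 6.1.1 share the problem only if they show best change, which is not stated.

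A reader might infer that the efficacy conclusion is at risk. It is not: ORR counts CR and PR and does not use DpR, the sample size rests on ORR, ETS uses the week 6 scan, and PFS has its own dating rules in Table A.

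**What to change.** Change the SAP only. In 4.2, 6.2.1 and 6.10, state: *DpR is the largest percentage reduction from baseline in the centrally read sum of diameters over post-baseline scans up to and including the first RECIST 1.1 progression by central review.* The central date is the right one because the sums are central reads. If the waterfall plots show best change, use the same scans for them.

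The cost is one sentence in three sections. No protocol amendment and no new data are needed, since all images already go to central review. The one downside is that target-lesion shrinkage after a centrally read new lesion no longer counts, so DpR may look slightly less favourable.
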